12.2. Blinding

There is no blinding in this protocol.

[figure not shown]

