7.3. Other Objectives and Endpoints

8. Study Design

This is a single-site, pilot, nonblinded randomized controlled performance evaluation to compare two brands of commercially-available single lumen PICC lines. This is a postmarket clinical evaluation and not a statistically powered study.

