10.5. Randomization

After consent and review of the inclusion/exclusion criteria, the Investigator can assign a randomization prior to baseline ultrasound. If during the ultrasound procedure, the subject meets an exclusion criterion, then this subject will be considered a screen fail.

[figure not shown]

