13.7. Ultrasound Measurements

Ultrasound methodology: The patient will be placed supine. Their palm will face upward with their arm abducted at 90° to conduct an ultrasound scan of the PICC line.

Ultrasonography will be performed on the vein that the PICC line is inserted. The vein will be scanned axially and transversely in two distinct sections. The first section is from insertion to the axillary junction. The second section is from the axillary junction to the superior vena cava

(SVC). The technician will pay particular attention to 2 cm above the insertion site, and at 10 cm above the insertion site as these will be specific data points to be recorded. The form used will have a picture of the vein and the technician can note where thrombosis was found. They will then measure the size of the thrombosis and note the approximate location in the form.

The diagnostic criteria will be based on any of the three US signs: (a) lack of normal vein compressibility, (b) lack of color signal from the vessel on the color Doppler scan, and (c) lack of signal from the vessel on the spectral Doppler scan. If technical problems or anatomical barriers hamper visualization, findings from the ultrasonographic screening will be considered indeterminate and appropriately recorded.

Based on ultrasound evaluation, veins will be classified as (1) without thrombosis or (2) with limited (2 to 4 mm), (3) large (~4 mm), or (4) occlusive thrombosis, as compared to baseline.

The person reading the ultrasound will use a data collection form to review the classification of the veins. The length and/or the depth of the thrombosis will be used to assess the classification. For example, if a thrombosis is 5mm long, but does not fully occlude the vessel, then it would be classified as a (3) large. However, if a thrombosis is 5mm long AND occludes the vessel, then it would be classified as a (4) occlusive thrombosis. The primary investigator will be responsible for confirming the classifications.

[figure not shown]

Image of veins from: (Chin, Zimmerman, & Grant, 2005)

14. Evaluations by Visit

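### Ultrasound grades are read and confirmed without masking, so the primary comparison is open to assessment bias; masked grading of coded clips would reduce it, not remove it

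*Combined protocol and SAP*

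**What the plan says.** Section 8 describes the design: "This is a single-site, pilot, nonblinded randomized controlled performance evaluation to compare two brands of commercially-available single lumen PICC lines". Section 12.2 adds: "There is no blinding in this protocol". Section 9.1, on minimizing bias, offers randomization by sealed envelope and nothing on outcome assessment.

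Under Section 10.5, after consent and the eligibility review, "the Investigator can assign a randomization prior to baseline ultrasound".

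Section 13.7 sets out the ultrasound work:

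- **Scan.** "Ultrasonography will be performed on the vein that the PICC line is inserted". If the technician finds a thrombosis, "They will then measure the size of the thrombosis and note the approximate location in the form".
- **Diagnosis.** Any one of three signs is enough: "lack of normal vein compressibility", absent colour signal, or absent spectral signal.
- **Grading.** There are four levels, assigned on length, depth or both, and compared with baseline. "The person reading the ultrasound will use a data collection form to review the classification of the veins".
- **Confirmation.** "The primary investigator will be responsible for confirming the classifications".

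Section 16.5.1 compares these results between arms with a Cochran-Armitage trend test on severity and Fisher's exact test on any thrombosis. Section 16.1 sets the level at two-sided 0.05.

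**The concern.** The grade involves judgement. The limited band runs from 2 to 4 mm and the large band is given as about 4 mm, so the two meet at the same figure, and length or depth may decide the class. Borderline calls of this kind are where knowing the device can act. The protocol also sets an expectation: Section 5.1 suggests the new material may lower thrombosis substantially, and Section 12.3 reports less thrombus in preclinical models.

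Randomization balances the patients but does not protect the reading. If borderline veins are called differently in the two arms, an observed difference, or the lack of one, cannot be put down to the catheter. With 10 analysed per arm, single readings carry weight. Placing the catheter openly does not require grading the scan openly, so part of this exposure is avoidable.

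**Working it through.** **Who can know the arm.** Set Sections 10.5 and 13.7 side by side. The Investigator assigns the randomization, and the primary investigator confirms the grade. The confirming role cannot be taken as unaware of the device. For the reader it is an inference: no section says the reader is told the arm, but none hides it, and Section 12.2 rules out blinding in general.

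**Is there a figure to reproduce?** No. The documents give no misreading rate, no bias estimate and no power calculation (Section 16.2). What follows is an assumed illustration.

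**Inputs.**
- n = 10 analysed per arm, 12 recruited (Section 10.7).
- Fisher's exact test, two-sided p ≤ 0.05 (Sections 16.1 and 16.5.1).
- True rate p = 0.4882 in both arms, the asymptomatic rate cited in Section 5.2.
- Assumed: a share m of HydroPICC thromboses read as clear, and a share f of clear comparator veins read as thrombosed, each 0.10 to 0.20.

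**Formulas.** Apparent HydroPICC rate = p(1 − m). Apparent comparator rate = p + (1 − p)f. Spurious difference = pm + (1 − p)f. The rejection probability is the sum of the two-binomial probabilities over all tables with Fisher p ≤ 0.05.

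| m | f | HydroPICC | Comparator | Difference (points) | Rejection, 10 per arm |
|---|---|---|---|---|---|
| 0 | 0 | 48.8% | 48.8% | 0 | 1.3% |
| 0.10 | 0.10 | 43.9% | 53.9% | 10.0 | 2.2% |
| 0.20 | 0.10 | 39.1% | 53.9% | 14.9 | 3.4% |
| 0.20 | 0.20 | 39.1% | 59.1% | 20.0 | 5.4% |
| 0.10 | 0 | 43.9% | 48.8% | 4.9 | 1.5% |
| 0.20 | 0 | 39.1% | 48.8% | 9.8 | 2.1% |

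Example, third row: 0.4882 × 0.8 = 0.3906; 0.4882 + 0.5118 × 0.1 = 0.5394; difference 0.1488.

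With 12 per arm, rejection is 2.3% without bias and about 4%, 6.1% and 9.7% in the three two-way cases.

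**What the table can and cannot show.** When m = f = x, the difference is px + (1 − p)x = x whatever p is. The 10 and 20 points in those rows simply restate the assumed error. The direction, favouring HydroPICC, is also assumed. The rejection rates are the part that is actually computed. They stay low at 10 per arm because Fisher's test is conservative at this size, so the main harm is a distorted rate difference rather than a false-positive test.

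**Weight of one reading.** 2/10 v 7/10 gives p = 0.070; 2/10 v 8/10 gives p = 0.023.

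**What masked grading would reach.** It covers classification and confirmation. It does not cover:
- detection, compression and measurement, which happen at the live scan by a technician who is with the patient;
- the judgement that a patient is free of symptoms, which Section 5.2 makes part of the definition;
- the unscheduled scans in Section 7.1, which follow clinical suspicion.

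**The case against.** The study declares openly that it is nonblinded. It is an unpowered pilot meant to test whether the ultrasound endpoint is feasible (Section 16.2), and Section 16.1 says it is not intended to support claims. Section 13.7 already limits free judgement through three named signs, comparison with baseline, a data form, an indeterminate category and confirmation by a second role. The visit lists in Section 14 require pictures of the insertion site only, and storage of ultrasound clips is not described, so masked reading takes more than a change of wording.

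Most of this stands, and it limits the severity. It does not dispose of the point. Structured criteria are not masking, and the arms will still be compared by prespecified tests. A pilot of an ultrasound endpoint is also a natural place to try masked reading before a larger study.

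A reader might infer that having the same staff read coded images would largely remove the bias. The documents do not support that. A later reading inherits what an unmasked operator looked for, recorded and measured. Images labelled by subject and scan date could be linked to the arm at one site with 24 subjects. Staff may recall cases, and the catheter lies in the scanned vein and may be recognisable. A reader might also infer that the results will be biased toward HydroPICC by 10 to 20 points; neither that direction nor that size is in the documents.

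**Conclusion.** The point holds in limited form. The primary comparison is open to assessment bias because the judged grade is confirmed by a role that cannot be presumed unaware of the device, and no section keeps the device from the reader. Masked grading would reduce this bias at the classification and confirmation steps and would not remove it.

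The size rests on assumption alone. Under two-way misreading of 10-20%, the spurious difference is 10 to 20 points and Fisher rejection at 10 per arm is 2.2-5.4%, against 1.3% without bias. With misses in one arm only, it is about 5 to 10 points and 1.5-2.1%. The change is worth making because it is cheap, and the pilot purpose keeps it below an essential correction.

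**What to change.** Amend Sections 12.2 and 13.7 as follows:

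1. Keep open-label insertion, and keep the live read for patient care.
2. Save compression, colour and spectral clips at each scheduled and unscheduled scan by a standard capture rule.
3. Label the clips with a random reading code that cannot be linked to subject, date or arm. Existing staff who do not grade hold the key.
4. Have the existing reader grade the clips, and the primary investigator confirm the grades, in batches and without the allocation. State that these masked grades are the ones analysed under Section 16.5.
5. Cover the hub and dressing during the scan where practical.
6. Report the live scan, symptom status and suspicion-triggered scans as steps that remain unmasked.

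**Cost.** No added staff and no added scans. The price is clip capture and storage, coding and some reading time. Masking stays partial, since the catheter may be recognised on the clip and staff at a small single site may remember cases.

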12.3. Description of HydroPICC

The HydroPICC peripherally inserted central catheter (PICC) is commercially available a single lumen catheter comprised of a radiopaque, hydrophilic base with a suture wing, Luer lock hub, and extension tube. The catheter has a maximum power injection rate of 3.5 mL/sec. The maximum usable length of the catheter is 55cm.

[figure not shown]
HydroPICC has been shown to be effective in reducing thrombus accumulation when evaluated using *in vitro* and *in vivo* models. Pre-clinical *in vitro* and *in vivo* evaluations to not necessarily predict clinical performance with respect to thrombus formation.

HydroPICC is manufactured and commercialized by Access Vascular, Inc.

HydroPICC Kit Components

HydroPICC Kit Components (continued)

12.4. Description of Comparator Product

The [REDACTED] is manufactured by [REDACTED]. According to their IFU, [REDACTED]

13. Study Procedures

13.1. Demographics

Demographic information will be recorded at Screening after a subject has signed the consent. This will include, but not limited to:

- Date of birth
- Race
- Ethnicity
- Gender

13.2. Medical History

Relevant medical history, including history of current disease, other pertinent venous history, and information regarding underlying diseases will be recorded at Screening.

13.3. Physical Examination

A complete physical examination will be performed by either the investigator or a sub-investigator who is a physician at Visit 1. Qualified staff (MD, NP, RN, and PA) may complete the abbreviated physical exam at all other visits. New abnormal physical exam findings must be documented and will be followed by a physician or other qualified staff at the next scheduled visit.

13.4. Vital Signs

Body temperature, blood pressure, Oxygen levels, heart rate and respirations will be performed. Blood pressure is only to be performed in the supine position on the non-treatment appendage in the study.

13.5. Concomitant Medications

All concurrent therapies will be documented at Screening, at follow up visits, and at early termination when applicable. Dose, route, unit frequency of administration, and indication for administration and dates of medication will be captured.

13.6. Clinical Laboratory Measurements

13.6.1. Laboratory Safety Measurements

Safety laboratory tests for this study [e.g. chemistry, hematology, coagulation (for applicable subjects), and urinalysis] are to be performed by the local institution per their standard of care.

13.6.2. Pregnancy Test

A urine or serum pregnancy test will be obtained from female subjects who are of childbearing age prior to their participation in the study. If a positive test returns, they are to be excluded.

All subjects will be urged to use birth control during the length of the study, however, if a subject does become pregnant during the length of the study, this will be noted, and data can continue to be collected if the Investigator deems it safe. All pregnancy related adverse events will be collected, but will be classified as pregnancy related.

13.7. Ultrasound Measurements

Ultrasound methodology: The patient will be placed supine. Their palm will face upward with their arm abducted at 90° to conduct an ultrasound scan of the PICC line.

Ultrasonography will be performed on the vein that the PICC line is inserted. The vein will be scanned axially and transversely in two distinct sections. The first section is from insertion to the axillary junction. The second section is from the axillary junction to the superior vena cava

(SVC). The technician will pay particular attention to 2 cm above the insertion site, and at 10 cm above the insertion site as these will be specific data points to be recorded. The form used will have a picture of the vein and the technician can note where thrombosis was found. They will then measure the size of the thrombosis and note the approximate location in the form.

The diagnostic criteria will be based on any of the three US signs: (a) lack of normal vein compressibility, (b) lack of color signal from the vessel on the color Doppler scan, and (c) lack of signal from the vessel on the spectral Doppler scan. If technical problems or anatomical barriers hamper visualization, findings from the ultrasonographic screening will be considered indeterminate and appropriately recorded.

Based on ultrasound evaluation, veins will be classified as (1) without thrombosis or (2) with limited (2 to 4 mm), (3) large (~4 mm), or (4) occlusive thrombosis, as compared to baseline.

The person reading the ultrasound will use a data collection form to review the classification of the veins. The length and/or the depth of the thrombosis will be used to assess the classification. For example, if a thrombosis is 5mm long, but does not fully occlude the vessel, then it would be classified as a (3) large. However, if a thrombosis is 5mm long AND occludes the vessel, then it would be classified as a (4) occlusive thrombosis. The primary investigator will be responsible for confirming the classifications.

[figure not shown]

Image of veins from: (Chin, Zimmerman, & Grant, 2005)

14. Evaluations by Visit

14.1. Screening Visit (Visit 1)

1. Assign the subject a unique screening number.
2. Perform informed consent process; subjects to sign and date the Informed Consent Form.
3. Record demographics data.

4. Record medical history, including a history of condition(s) requiring chemotherapy or antibiotics, diagnosis date, and prior treatments related to the relevant condition(s).
5. Record baseline labs, if available.
6. Perform a complete physical examination.
7. Perform and record vital signs.
8. Schedule subject for Procedure visit in no more than 5 days
9. Randomize the subject

14.2. Surgical Visit- (Visit 2)

1. Perform and record vital signs.
2. Record labs, if available.
3. Conduct Ultrasound prior to insertion of the assigned PICC. Screen fail if necessary.
4. Insert device per assigned randomization, IFU, and institutional procedures.
5. Confirm patient entry into study.
6. Take picture of insertion site.
7. Record adverse events (if any).

14.3. Follow Up Visit- (Visit 3) (7 days post placement ± 5 days)

1. Perform and record vital signs.
2. Record Adverse Events (if any).
3. Record changes to concomitant medications (if any).
4. Record labs, if available.
5. Conduct ultrasound assessment of treatment extremity.
6. Take picture of insertion site.

14.4. Follow Up Visit- (Visit 4) (14 days post placement ± 7 days)/ MUST be at least 4 days after the Visit 3

7. Perform and record vital signs.
8. Record Adverse Events (if any).
9. Record changes to concomitant medications (if any).
10. Record labs, if available.
11. Conduct ultrasound assessment of treatment extremity.
12. Take picture of insertion site.
13. Complete the end of study CRF. Indicate reason for end of study (completion of study, therapy, or otherwise).

14.5. Unscheduled Visit(s)

1. Perform and record vital signs.
2. Record Adverse Events (if any).
3. Record changes to concomitant medications.
4. Record labs, if available.
5. Conduct ultrasound assessment of treatment extremity.
6. Take picture of insertion site.
7. Remove or treat the PICC line per IFU and institutional protocols if necessary.
8. If a subject is discontinued from the study due to a Serious Adverse Device Effect, the institution should notify their IRB per the IRB reporting requirements.

15. Adverse Event Reporting

These definitions are for the purposes of this post market clinical evaluation only. Medical Device Reporting (MDR) will be conducted using the normal AVI definitions for reporting to the FDA. We will follow [REDACTED].

Adverse Event (AE) (ISO 14155:2020): untoward medical occurrence, unintended disease or injury, or untoward clinical signs (including abnormal laboratory findings) in subjects, users or other persons, whether or not related to the investigational medical device and whether anticipated or unanticipated.

Note 1: This definition includes events related to the investigational medical device or the comparator.

Note 2: This definition includes events related to the procedures involved.

Note 3: For users or other persons, this definition is restricted to events related to the use of investigational medical devices or comparators.

Adverse Device Effect (ADE) (ISO 14155:2020): is an adverse event that is related to the use of an investigational medical device.

Note 1: This definition includes adverse events resulting from insufficient or inadequate instructions for use, deployment, implantation, installation or operation, or any malfunction of the investigational medical device.

Note 2: This definition includes any event resulting from use error or from intentional misuse of the investigational medical device.

Note 3: This includes "comparator" if the comparator is a medical device.

Comparator: medical device, therapy (e.g. active treatment, normal clinical practice), placebo or no treatment, used in the control group in a clinical investigation.

Serious Adverse Event (ISO 14155:2020):

A Serious Adverse Event (SAE) is an adverse event that:

- a) Led to death,
- b) Led to serious deterioration in the health of the subject, users, or other persons as defined by one or more of the following: 1) A life-threatening illness or injury, or
- 2) A permanent impairment of a body structure or a body function including chronic diseases, or
- 3) In-patient or prolonged hospitalization, or
- 4) Medical or surgical intervention to prevent life-threatening illness or injury or permanent impairment to a body structure or a body function,
- c) Led to fetal distress, fetal death or a congenital abnormality or birth defect including physical or mental impairment

Note: Planned hospitalization for a pre-existing condition, or a procedure required by the study protocol, without serious deterioration in health, is not considered a serious adverse event.

Serious Adverse Device Effect (SADE): A Serious Adverse Device Effect (SADE) is an adverse device effect that has resulted in any of the consequences characteristic of a serious adverse event

AE Severity

The National Cancer Institute's Common Terminology Criteria for Adverse Events (CTCAE) Version 5.0 should be used to assess and grade AE severity, including laboratory abnormalities judged to be clinically significant (US Department of Health and Human Services, 2017). The modified criteria can be found in ~~The study plan should be expanded to include a severity scale that is based on the modified CTCAE criteria. The modified CTCAE criteria is a measure of intensity and that a severe AE is not necessarily serious.~~

~~The study plan should be expanded to include a severity scale that is based on the modified CTCAE criteria. The modified CTCAE criteria is a measure of intensity and that a severe AE is not necessarily serious.~~

Table 1. AE Severity Grading

A Prospective, Randomized PICC Asymptomatic Thrombosis Study (PROPATH)	Number: 20-002
	Version: C 28Apr2021
	Page: 23 of 30

Severity (Toxicity Grade)	Description
Mild (1)	Asymptomatic or mild symptoms; clinical or diagnostic observations only; intervention not indicated.
Moderate (2)	minimal, local or noninvasive intervention indicated; limiting age appropriate instrumental ADL*.
Severe (3)	Severe or medically significant but not immediately life-threatening; hospitalization or prolongation of hospitalization indicated; disabling; limiting self care ADL**
Life-threatening (4)	Life-threatening consequences; urgent intervention indicated.
Death (5)	Death related to AE

Activities of Daily Living (ADL)

*Instrumental ADL refer to preparing meals, shopping for groceries or clothes, using the telephone, managing money, etc.

**Self care ADL refer to bathing, dressing and undressing, feeding self, using the toilet, taking medications, and not bedridden.

AE Relationship to Device

The relationship of an AE to the study device should be assessed using the following the guidelines in Table 2.

Table 2. AE Relationship to Study Device

Relationship to Device	Comment
Definitely	Previously known hazard related to this class and type of device; or an event that follows a reasonable temporal sequence from implantation of the device; that follows a known or expected response pattern to the suspected device; that is confirmed by stopping and removal of the device; and that is not explained by any other reasonable hypothesis.
Probably	An event that follows a reasonable temporal sequence from implantation of the device; that follows a known or expected response pattern to the device; that is confirmed by stopping or removal of the device; and that is unlikely to be explained by the known characteristics of the subject's clinical state or by other interventions.
Possibly	An event that follows a reasonable temporal sequence from implantation of the device; that follows a known or expected response pattern to that device; but that could readily have been produced by a number of other factors.
Unrelated	An event that can be determined with certainty to have no relationship to the study device.

AE Relationship to Study Procedure

The relationship of an AE to the study procedure should be assessed using the following the guidelines in Table 3.

Table 3. AE Relationship to Study Procedure

Relationship to Device	Comment
Definitely	Previously known hazard related to this procedure; or an event that follows a reasonable temporal sequence from the procedure; that follows a known or expected response pattern to the suspected procedure; that is confirmed by stopping the procedure; and that is not explained by any other reasonable hypothesis.

Probably	An event that follows a reasonable temporal sequence from the procedure; that follows a known or expected response pattern to the procedure; that is confirmed by stopping the procedure; and that is unlikely to be explained by the known characteristics of the subject's clinical state or by other interventions.
Possibly	An event that follows a reasonable temporal sequence from the procedure; that follows a known or expected response pattern to the procedure; but that could readily have been produced by a number of other factors.
Unrelated	An event that can be determined with certainty to have no relationship to the procedure.

